5.6.4 Loss to follow-up

For subjects whose status is unclear because they fail to appear for study visits without stating an intention to discontinue or withdraw, the investigator should show "due diligence" by documenting in the source documents steps taken to contact the subject, e.g. dates of telephone calls, registered letters, etc. A subject cannot be considered as lost to follow-up until the time point of his/her scheduled end of study visit (Week F120) has passed.

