9.4.3 Handling of missing values/censoring/discontinuations

Missing Week 104 data for a given subject will be imputed using an imputation model based on the observed data of subjects in the same randomized arm who also discontinued the study treatment but for whom Week 104 X-ray data is available ('retrieved dropout approach') and based on the observed data of the given subject (Baseline and Week 52).

The potential sparsity of the retrieved data may preclude fitting the proposed imputation model to impute the subjects with missing X-ray data at Week 104. In this case, an alternative approach may be used if necessary, which will be detailed in the statistical analysis plan.

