### 2.5.3 Handling of missing values/censoring/discontinuations

Missing Week 104 data for a given subject who discontinued in the study will be imputed using an imputation model based on the observed data of subjects in the same randomized arm who also discontinued study treatment but for whom Week 104 X-ray data are available ('retrieved dropout approach', [EMA 2010](#)) and based on the observed data of the given subject.

A logistic regression model will be fitted to the Week 104 X-ray data for the retrieved dropout patients, while adjusting for treatment, baseline mSASSS and post-baseline slope in mSASSS.

The post-baseline slope is defined as the last available post-baseline change in mSASSS score divided by study day on which the X-ray was taken. Recent literature suggests that in AS patients treated with TNF inhibitors the spinal radiographic progression followed a linear course during the first 4 years of follow-up (Maas, et. al. 2017). Thus, the linearity assumption is expected to be reasonable. The covariates of baseline mSASSS and slope will be standardized to have a mean of 0 and standard deviation of 1 before model fitting.

PROC MCMC will be used for fitting the logistic regression model and multiple imputation of the Week 104 value, with weakly informative priors and model code as shown below,

```
prior beta1 ~ normal(0,sd=2);
```

```
prior beta2 ~ normal(0,sd=2);
```

```
prior beta3 ~ normal(0,sd=2);
```

```
prior beta4 ~ normal(0,sd=3);
```

```
prior beta5 ~ normal(0,sd=3);
```

```
pi = logistic(beta1*trt_GP2017 + beta2*trt_SEC150 + beta3*trt_SEC300 +  
beta4*sqrt(base_stand) + beta5*slope_stand);
```

```
model noprog ~ binary(p = pi);
```

where trt\_GP2017 – binary indicator for GP2017 40 mg

trt\_SEC150 – secukinumab 150 mg

trt\_SEC300 – secukinumab 300 mg

sqrt(base\_stand) – square root of the baseline mSASSS (standardized)

slope\_stand – the last available post-baseline change in mSASSS score divided by study day on which the X-ray was taken (standardized)

noprog – no radiographic progression at Week 104

If all post-baseline values are missing for a subject, the subject will be imputed based on a similar model as above but just based on treatment and baseline value as covariates (without the post-baseline slope variable). Subjects with a missing baseline will be excluded from the analysis.

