Missing Week 104 data due to an incomplete number of interpretable locations for a given subject will be imputed using the same imputation model as described above but based on the observed data of all subjects who provided Week 104 data and based on the observed data of the given subject.

In this way multiple complete data sets are created and for each of these completed datasets the response rate will be calculated and then combined using Rubin's rule.

The potential sparsity of the retrieved data may preclude fitting the proposed model to impute the subjects with missing X-ray data at Week 104. In this case, a fallback approach will be utilized.

In case of low sample size of the retrieved dropout data (< 8 for any treatment group), the imputation model can lead to unstable imputations. In this case imputations will be performed based on a model without treatment as a covariate.

$$pi = \text{logistic}(\text{beta1} + \text{beta4} * \text{sqrt}(\text{base\_stand}) + \text{beta5} * \text{slope\_stand})$$

In case there are less than 8 retrieved dropout patients overall, the same imputation model as above will be used (without treatment as a covariate) but based on all patients (not only retrieved dropout patients).

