### 2.6.3 Handling of missing values/censoring/discontinuations

Missing Week 104 change from baseline values in mSASSS for a given subject will be imputed using an imputation model based on the observed data of subjects in the same randomized arm who also discontinued study treatment but for whom Week 104 X-ray data are available (‘retrieved dropout approach’, EMA 2010). Recent literature suggests that in AS patients treated with TNF inhibitors, the spinal radiographic progression followed a linear course during the first 4 years of follow-up (Maas, et. al. 2017). Therefore, a parametric model assuming a normal distribution and a linear time trend for the mean scores will be used to impute missing Week 104 values. The model will be fitted to the average of the three readers’ change from baseline in mSASSS.

We will consider a mixed-effects model for the change in mSASSS functional scale measurement. Let  $y_{ij}$  be the  $j^{\text{th}}$  change from baseline measurement of subject  $i$ , at time  $t_{ij}$ :

$$y_{ij} = \alpha_i t_{ij} + \epsilon_{ij} \text{ with } \epsilon_{ij} \sim N(0, \sigma^2).$$

The subject specific intercept  $\alpha_i$  will be modelled using treatment and the subject's baseline mSASSS value as fixed effects and assuming a subject-specific normally distributed random effect.

PROC MCMC will be used for fitting the mixed-effects model and multiple imputation of the Week 104 value, with weakly informative priors and model code as shown below,

```
random gamma ~ normal(0, sd=sd_re) subject=usubjid;
prior beta1 ~ normal(0,sd=100);
prior beta2 ~ normal(0,sd=100);
prior beta3 ~ normal(0,sd=100);
prior beta4 ~ normal(0,sd=100);
prior beta5 ~ normal(0,sd=100);
prior sd_re ~ uniform(0,20);
prior sd ~ uniform(0,20);
mu = (beta1*trt_GP2017 + beta2*trt_SEC150 + beta3*trt_SEC300 + beta4*base +
beta5*sq_base_stand + gamma)*ady/365.25;
model chg ~ normal(mu, sd=sd);
```

where trt\_GP2017 – binary indicator for GP2017 40 mg

trt\_SEC150 – binary indicator for secukinumab 150 mg

trt\_SEC300 – binary indicator for secukinumab 300 mg

base – baseline mSASSS

sq\_base\_stand – square root of baseline mSASSS (standardized)

gamma – random effect

ady – number of days when X-ray assessment was done after randomization

chg – change from baseline in mSASSS at Week 104

For absence of new syndesmophytes at Week 104, the handling of missing data will be the same as the primary endpoint.

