## 4 Change to protocol specified analyses

No change from protocol specified analysis was made.

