For the datasets generated with the PROC MCMC routine, the same analysis as described in this section will be performed. PROC MCMC will be run twice with 100000 iterations, a thinning of 1000, and burn-in of 10000 in order to obtain 200 partially completed datasets. 100 datasets will have imputed data for subjects who discontinued the study, and the other 100 datasets will have imputed data for subjects with missing data for other reasons (e.g., due to an incomplete number of interpretable locations). The two sets of 100 partially completed datasets will be patched together matching their iteration number. That is, the datasets corresponding to the  $i$ -th iteration of the first 100 datasets will be merged with the datasets corresponding to the  $i$ -th iteration of the second 100 datasets. The SAS code below outlines a template for the procedure:

```
PROC MCMC data= seed=4572340 nbi=10000 nmc=100000 thin=1000
missing=CCMODEL;
    parms beta1 beta2 beta3 beta4 beta5;
    prior beta1 beta2 beta3 ~ normal(0,var=2);
    prior beta4 beta5 ~ normal(0,var=3);
    pi = logistic(beta1 * trt_GP2017 + beta2 * trt_SEC150 + beta3 * trt_SEC300 + beta4 *
sqrt(base_stand) + beta5 * slope_stand);
    model y ~ binary(pi);
    preddist outpred=;
run;
```

Analogous codes will be used to impute the missing data due to other reasons (other than study discontinuation) as well as the change from baseline in mSASSS at Week 104 (secondary endpoint).

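### The SAP chooses imputation donors by study status rather than treatment status, so some off-treatment subjects are imputed from mainly on-treatment donors

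*SAP*

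**What the plan says.** - **Protocol 9.4.3** has a single rule for missing Week 104 data. Donors are subjects in the same randomized arm "who also discontinued the study treatment but for whom Week 104 X-ray data is available". The subject's own observed data are also used. Recipients are not split by study status.
- **SAP 2.5.3** opens with "Missing Week 104 data for a given subject who discontinued in the study will be imputed", again from treatment discontinuers with a Week 104 film. It adds a second stream: data missing because too few locations could be read are imputed with the same model, but "based on the observed data of all subjects who provided Week 104 data". Treatment status is not a condition of that stream.
- **SAP 5.4.3.2** fixes the split when it describes the two runs: "100 datasets will have imputed data for subjects who discontinued the study", and the other 100 cover all other reasons, with uninterpretable locations given as an example. It then repeats that the second group is defined by not being study discontinuation.
- **The imputation model** in SAP 2.5.3 contains arm, baseline mSASSS and post-baseline slope. It has no on/off-treatment term.
- **SAP section 4** states: "No change from protocol specified analysis was made".

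**The concern.** The protocol keeps stopping treatment apart from leaving the study, and its visit-schedule section encourages subjects who stop treatment to stay. It therefore expects a group of off-treatment subjects who remain under observation. The retrieved-dropout method is there so that members of this group with no usable Week 104 result are imputed from outcomes seen after stopping. That is what the estimand needs, since it counts subjects whether or not they kept to their assigned treatment.

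When recipients are sorted by study status, an off-treatment subject who stayed but has an uninterpretable film falls into the all-subject stream. With no on/off term in the model, that subject gets a prediction dominated by subjects still on treatment. What is at stake is a small upward shift in the secukinumab no-progression rate in the confirmatory analysis, and a departure from the protocol that the SAP does not declare.

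**Working it through.** **Inputs (SAP section 3; the same figures are in protocol 9.7).** n = 279 per arm; 80% complete treatment with both films evaluable; no-progression rate 66% on secukinumab, 51% after stopping treatment, 51% for GP2017; two-sided alpha 0.025 per dose.

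**Reproducing the plan's figures.**
- Diluted secukinumab rate: 0.80 × 66% + 0.20 × 51% = 52.8% + 10.2% = 63.0% (stated 63%).
- Power for 63% against 51%, mean rate 0.57: (0.12 × √279 − 2.2414 × √(2 × 0.57 × 0.43)) / √(0.63 × 0.37 + 0.51 × 0.49) = (2.004 − 1.569) / 0.695 = 0.626, so power is 0.734 (stated about 73%).

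The sample size is not in question. These rates simply give a consistent basis for sizing the routing effect.

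**Who is in the all-subject donor pool.** On-treatment donors per secukinumab arm: 0.80 × 279 = 223.2. Off-treatment: 0.20 × 279 = 55.8. Let r be the number of off-treatment subjects who do give a Week 104 film; the documents do not state it.
- Pool rate = (223.2 × 66% + r × 51%) / (223.2 + r).
- 25% retrieved (r = 14.0): pool 65.1%, of which 94% on treatment.
- 50% retrieved (r = 27.9): pool 64.3%, 89% on treatment.
- 75% retrieved (r = 41.9): pool 63.6%, 84% on treatment.

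**Effect on the secukinumab rate.** If m off-treatment subjects per arm are imputed from this pool instead of at 51%, the shift is m × (pool rate − 51%) / 279. The documents do not give m, so it is an assumption.

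With the pool set at the plan's overall 63%, slightly below the values above:
- m = 5: 5 × 12 / 279 = 0.22 points
- m = 14: 14 × 12 / 279 = 0.60 points
- m = 28: 28 × 12 / 279 = 1.20 points

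With the pool rate computed and half of off-treatment subjects retrieved, 27.9 remain without a result:
- a quarter of them in the study (m = 7.0): 7.0 × 13.3 / 279 = 0.33 points
- half of them in the study (m = 14.0): 0.67 points

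GP2017 does not move, because the plan uses 51% on and off treatment.

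**Scale.** The standard error of the difference is √((0.63 × 0.37 + 0.51 × 0.49) / 279) = 4.2 points. A shift of 0.33 is about 0.08 of that, and 1.2 about 0.3.

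All of this ignores baseline mSASSS and the subject's own slope. Both are in the model and would take up part of the difference.

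**The case against.** **The main text is ambiguous.** The opening of SAP 2.5.3 could be read as meaning subjects who stopped treatment, since its donors are described as having also done so. This stands for 2.5.3 taken alone. But 5.4.3.2 defines the split by study discontinuation twice, and the stream for uninterpretable films carries no treatment condition on any reading.

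**A subject with no film at all.** The SAP names no donor pool for a subject who stayed in the study but was never imaged. All-subject donors are an inference from 2.5.3 and 5.4.3.2 together, and should be described as one.

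**The effect is small and partly guarded against.** This stands. Partly missing films are first completed at unit level (SAP 5.1), and the Week 104 X-ray window is wide (days 640 to 849), so few subjects may be affected. The tipping point analysis in SAP 2.5.4 varies all missing responses, though it does not correct the primary estimate. With fewer than 8 retrieved dropouts overall, the fallback makes all patients the donors and the two streams coincide. For that reason a shift of 3 points (63% to 66%), which would need no retrieved dropouts at all, should not be relied on.

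**Stronger readings that the documents do not support:**
- A reader might infer that imputing a subject who took every dose and then left from treatment discontinuers also breaches the protocol. Protocol 9.4.3, read literally, gives exactly those donors.
- A reader might infer that the primary hypotheses (H1, H2) and the mSASSS change (H3, H4) certainly use different donors, because SAP 2.6.3 begins "Missing Week 104 change from baseline values in mSASSS for a given subject will be imputed" and mentions only the retrieved-dropout pool. The closing sentence of 5.4.3.2 plausibly extends the two-run procedure to the mSASSS change, so this is unclear wording, not an established conflict.
- Protocol 5.6.4 says: "A subject cannot be considered as lost to follow-up until the time point of his/her scheduled end of study visit (Week F120) has passed". A reader might infer that subjects who vanish are put in the wrong stream at a Week 104 lock. Nothing ties the imputation flag to that label, and the Week 104 analysis is only optional.

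**Conclusion.** The point holds for subjects who permanently stopped treatment, stayed in the study and have too few interpretable locations at Week 104. They are imputed mainly from on-treatment donors, contrary to protocol 9.4.3 and without a declaration in SAP section 4. Subjects in the same position with no film appear to be treated the same way, by inference.

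On the plan's rates the secukinumab rate is overstated by about 0.2 to 1.2 points for 5 to 28 such subjects per arm, and more likely by a few tenths. This rests on assumed counts, on the 66% and 51% rates, and on ignoring the covariates. The plan's remaining 20% may also include treatment completers with unreadable films, so 56 per arm is a loose ceiling for the off-treatment group. The direction given is for this group only; the net effect of all missing-data handling is not established. The shift is too small to change the trial's prospects by itself. It is worth correcting because it lies in the primary analysis, leans towards the sponsor's product and is cheap to remove.

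**What to change.** Before database lock:
- In SAP 2.5.3 and 5.4.3.2, define the first stream by treatment status. Any subject with missing Week 104 mSASSS data who permanently discontinued study treatment early goes to the retrieved-dropout donors, whether or not they left the study and whatever the reason for the missing result.
- Name the donor pool for a subject who stayed in the study but has no Week 104 film.
- State in SAP 2.6.3 that the same routing applies to the mSASSS change. Absence of new syndesmophytes already follows the primary endpoint.
- List in SAP section 4 any departure from protocol 9.4.3 that is kept, such as all-subject donors for treatment completers with unreadable films.

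The cost is a few sentences and one recoded flag; dosing dates and the reason for stopping are already on the CRF. The downside is slightly higher imputation variance, because more subjects draw on the smaller donor pool.

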#### 5.4.4 Crude incidence and related risk estimates

##### 5.4.4.1 Crude incidence and $100*(1-\alpha)\%$ confidence interval

For  $n$  subjects, each at risk to experience a certain event with probability  $\pi$ , the crude incidence is estimated as  $p=x/n$ , where  $x$  is the number of subjects with the event.

Absolute and relative frequencies will be displayed as well as 95% confidence interval for the relative frequency based on the score method including continuity correction ([Newcombe 1998](#)).

With  $z$  as  $(1-\alpha/2)$ -quantile of the standard normal distribution (SAS:  $z=PROBIT(1-\alpha/2)$ ),  $n$  as total number of subjects (i.e., number of subjects in the denominator), and  $p$  as estimated crude incidence (number of subjects with event /  $n$ ) it is  $q=1-p$ .

Then the lower limit is

$$L = \max \left( 0, \frac{2np + z^2 - 1 - z\sqrt{z^2 - 2 - \frac{1}{n} + 4p(nq+1)}}{2(n+z^2)} \right)$$

and the upper limit is

$$U = \min \left( 1, \frac{2np + z^2 + 1 + z\sqrt{z^2 + 2 - \frac{1}{n} + 4p(nq-1)}}{2(n+z^2)} \right).$$

Note: If  $L > p$  then  $L = p$  and if  $U < p$  then  $U = p$ .

If appropriate, an exact  $100*(1-\alpha)\%$  confidence interval (Clopper-Pearson 1934) will be obtained by using the SAS procedure PROC FREQ with the EXACT BINOMIAL statement. However, the confidence interval derived via the score method including continuity correction will be the default in safety analyses.

